**Document date: 02-17-2023** 

## Statistical Analysis Plan

First, descriptive statistics were calculated to describe the characteristics of the study participants at baseline, 4-week follow-up, and 3-month follow-up. Wilcoxon rank-sum tests were used to compare continuous/numeric variables between the control and intervention groups at each visit. Fisher's exact tests were used to compare categorical variables. No adjustments have been made for multiple comparisons. After that, Wilcoxon rank-sum tests were used to compare percent and raw score change in the primary outcomes between baseline and 4 weeks and baseline and 3 months in the study and control groups.

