The study consists of two phases corresponding to two aims. For Aim 1 we will develop a modularized, functionally-tailored oral care intervention based on literature review and CG interview input. We anticipate eight training modules that can be used alone or in varying combinations to provide functionally-appropriate oral care rehabilitation for PWD and needbased skills training to their family CGs. These will be adapted from Mouth Care Without a Battle, a validated oral hygiene intervention developed for NH residents with dementia. Aim 2 will examine the efficacy and feasibility of the proposed intervention using a randomized controlled design among 40 PWD/CG pairs. After baseline assessment, a 4-week, dyadic, hands-on, functionally-tailored oral care intervention will be delivered to 20 PWD/CG dyads. Control group participants (n=20) will receive the oral hygiene education that is commonly provided to PWD during dental care. Data collection will occur at baseline, 4-weeks and 3 months. Differences between the control and intervention groups with regard to PWD outcomes (e.g., oral hygiene and behavior symptoms during oral care), caregiver outcomes (e.g., burden, self-efficacy) and the care partner relationship will be explored.

This protocol has been developed to guide the study of Aim I and the Aim II study.

IV. Eligibility, Enrollment, and Consent

Sources of Recruitment. Tentatively, the study participants will be recruited from the sites listed below. The site names and IDs are as follows:

Table 2 recruitment sites and ID

Recruitment site	Site ID
Phase I study	10
Dementia registry	20
UI Memory Care Clinic ([name])	30
UI Dental School	40
UI Geriatric Clinic ([name]/[name])	50
Local Community (mass email)	60
UIHC list (TrinetX)	70
Mercy Caregiver Group	80
Huntington's Clinic	90
Mercy Center for Memory Health	11
Heritage Area Agency on Aging	12

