Apathy	Dementia Apathy Interview and Rating	FCG	Baseline	RA
Anosognosia	AnosognosiaSelf-perceived oral health	PWD/FCG	Baseline	RA
Oral hygiene	Plaque index Gingival index	PWD	Baseline 4-week follow-up 3-month follow-up	Dentist
 Sociodemographics Medical history & medication Dental care pattern 	Caregiver Interview	FCG	Baseline	RA OCC
 Oral hygiene practice Perceived oral hygiene and oral health Behavior symptoms during oral care Mouth Care Related Caregiver Burden Dyadic relationship 	Caregiver Interview	FCG	Baseline4-week follow-up3-month follow-up	LD &RA
CG efficacy in providing oral care	Caregiver Self-efficacy Scale	FCG	Baseline4-weekfollow-up3-monthfollow-up	RA
First visit assessment	First visit assessment form	PWD/FCG	1 st visit	LD
Feasibility assessment (session)	 Care recipient Feasibility Evaluation Questionnaire Caregiver Feasibility Evaluation Questionnaire 	PWD/FCG	Every session	LDRA
Trainer assessment	Trainer evaluation questionnaire	Trainer	Every session	LD
Daily oral care practice	Daily oral care log	PWD/FCG	Every session3-month follow-up	LD

Feasibility assessment (program)	•	Care recipient Program Feasibility Evaluation Questionnaire Caregiver Feasibility Program Evaluation Questionnaire	PWD/FCG	4-week follow-up	RA
Implementation assessment	•	Training log & trainer interview	Trainer	Every session	XC

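### The SAP has no separate test for ordered categorical variables; if graded interview items go to Fisher's exact test, their order is ignored (minor point)

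*SAP*

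**What the plan says.** The single paragraph of the SAP (Statistical Analysis Plan) gives two routes by type of variable. For the first, "Wilcoxon rank-sum tests were used to compare continuous/numeric variables between the control and intervention groups at each visit". For the second, Fisher's "exact tests were used to compare categorical variables". It does not divide categorical variables into binary, unordered and ordered, and it does not list which variables fall under which heading. The phrase about each visit belongs to the rank-sum sentence; the Fisher sentence does not repeat it.

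Change in the primary outcomes has its own sentence: "Wilcoxon rank-sum tests were used to compare percent and raw score change in the primary outcomes". The SAP also states: "No adjustments have been made for multiple comparisons". Neither document gives a significance level, a power target or an effect size.

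Protocol section VII, Table 5, lists caregiver-interview items collected at baseline, 4 weeks and 3 months. They include oral hygiene practice and "Perceived oral hygiene and oral health". No response formats are printed. Protocol section III plans equal arms: "oral care intervention will be delivered to 20 PWD/CG dyads", and "Control group participants (n=20) will receive" the comparison education. It describes the between-group differences as something to be explored.

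**The concern.** Items on oral hygiene practice or perceived oral health are often answered on a short graded scale. Such an item is ordered, but it can easily be filed as categorical. On a table with two arms and three or more answer levels, Fisher's test returns the same p-value however the columns are shuffled. It therefore asks only whether the two distributions differ in some way. The trial asks whether the intervention moves answers in the better direction, and a test that uses the order puts its power there.

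With 40 dyads, power is scarce. A real shift on a graded item could be reported as no difference, and the item might then be dropped from later work.

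**Working it through.** **Inputs from the documents.** 20 dyads per arm (Protocol section III); Fisher's test for categorical and rank-sum for numeric variables (SAP). The plan states no power figure, so there is none to reproduce.

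**Assumed inputs.** Two-sided 5% level; no dropout; graded items with 3, 4 or 5 levels; a proportional-odds shift with odds ratio (OR) 2 to 7.

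**Model.** If C_j is the control probability of answering at level j or below, the intervention probability is C_j / [C_j + OR × (1 − C_j)]. Example: three equal levels and OR 2 give (1/3)/(1/3 + 4/3) = 0.20 and (2/3)/(2/3 + 2/3) = 0.50, so the intervention distribution is 20%, 30%, 50%.

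**Tests compared.** (a) Fisher's exact test extended to 2 × k tables (Fisher-Freeman-Halton). (b) The rank-sum test with mid-ranks, tie-corrected and continuity-corrected. There were 4,000 simulated trials per setting, so the standard error is at most √(0.25/4000) = 0.8 points.

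**Size under no effect.** Fisher 4.2% to 5.5%; rank-sum 4.6% to 5.5%. The simulation error here is √(0.05 × 0.95/4000) = 0.35 points, so both tests are close to nominal. The difference in power below therefore comes from ignoring order, not from a conservative level.

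**Power, Fisher v rank-sum (%).**

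| Control distribution | OR 2 | OR 3 | OR 4 | OR 5 | OR 7 |
|---|---|---|---|---|---|
| 3 equal levels | 14.8 v 20.5 | 32.0 v 42.5 | 49.0 v 61.1 | 59.2 v 72.4 | 75.5 v 85.1 |
| 3 levels, 50/30/20 | 14.2 v 20.0 | 34.4 v 44.9 | 51.4 v 63.6 | 64.2 v 75.0 | 81.4 v 89.2 |
| 4 equal levels | 14.7 v 22.2 | 31.6 v 46.2 | 46.4 v 64.2 | 58.7 v 76.2 | 76.0 v 89.5 |
| 4 levels, 40/30/20/10 | 13.7 v 21.8 | 30.2 v 46.2 | 46.2 v 64.9 | 61.0 v 77.9 | 78.6 v 90.4 |
| 5 equal levels | 13.6 v 22.2 | 28.1 v 46.8 | 44.4 v 66.2 | 56.9 v 76.8 | 73.4 v 89.4 |
| 5 levels, 10/20/40/20/10 | 12.2 v 21.7 | 26.0 v 46.4 | 40.5 v 64.8 | 54.3 v 77.5 | 73.2 v 90.4 |

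Smallest and largest gains by number of levels:
- 3 levels: 20.5 − 14.8 = 5.7 to 72.4 − 59.2 = 13.2 points.
- 4 levels: 22.2 − 14.7 = 7.5 to 64.9 − 46.2 = 18.7 points.
- 5 levels: 22.2 − 13.6 = 8.6 to 64.8 − 40.5 = 24.3 points.

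**Binary variables, as a side check.** All 21 × 21 outcomes at 20 v 20 were enumerated. The true size of Fisher's test peaks at 2.5%; that of Boschloo's unconditional exact test peaks at 4.6%. Power, Fisher v Boschloo: 40.9% v 49.2% (20% v 50%), 49.2% v 60.9% (10% v 40%), 59.9% v 70.5% (30% v 70%) and 94.4% v 97.1% (5% v 55%). Over the rates tried, Boschloo gains about 3 to 12 points.

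**The case against.** The strongest objection is that nothing in the documents assigns a graded item to Fisher's test. The SAP's numeric class can reasonably be read to include scored ordinal items, and much of Table 5 consists of indices and scales that yield scores. The plan may already do what is asked here. This stands, and it is why the point is conditional. What remains is that the SAP does not say how ordered items are classed, and on its plain wording an item treated as categorical goes to Fisher.

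A reader might infer more than the documents support:

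- *That a known amount of power is lost on named outcomes.* The documents give no level, response scale, rates or effect size. The clearly categorical items, such as sociodemographics and dental care pattern, are collected at baseline only in Table 5, where lost power costs little.
- *That Fisher's test is strongly conservative for every categorical variable.* That holds for 2 × 2 tables at this size. With three to five levels the test ran near 5%.
- *That Fisher's test is wrong for yes/no variables.* It is a valid small-sample default. Conditional against unconditional exact testing is a methodological preference, and no binary efficacy outcome is named.
- *That the primary comparison is weakened.* Change in the primary outcomes is already tested by rank-sum.

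A further objection is that changing a test after analysis, with no multiplicity adjustment, invites extra positive findings. For ordered items the per-test size barely moves, since both tests are near nominal. The post hoc nature of the change is nevertheless real and must be disclosed.

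**Conclusion.** The point holds as a conditional, minor one. The SAP makes no provision for ordered categorical variables. If graded interview items are analysed as categorical, Fisher's test discards their order and, in the scenarios tried, rank-sum would gain about 6 to 13 points of power with three levels, 8 to 19 with four and 9 to 24 with five. Those ranges rest on 20 analysed dyads per arm, a two-sided 5% level and proportional-odds shifts, all but the planned arm size being assumptions. If no graded item is treated as categorical, nothing is lost. The comparisons concerned are exploratory.

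**What to change.** Replace the SAP sentence on categorical variables with: *Ordered categorical variables will be compared by the Wilcoxon rank-sum test with mid-ranks; Fisher's exact test is kept for binary and unordered variables.* List which interview items count as ordered.

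The cost is one sentence and, if any graded item was in fact run through Fisher's test, a rerun on existing data with a method the SAP already uses. The downside is timing. The SAP is written as if the analysis were done, so changed results should be labelled as a revised analysis and reported beside the Fisher results, whichever way they move.

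Boschloo's test for binary variables is an optional extra and need not accompany this change.

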Once eligibility is identified for both FCG and PWD, the research team member will ask if the dyad are self-responsible for consenting to research. If they are not, the research team member will ask for LAR contact information and proceed to contact the LAR, explain the study, and mail the informed consent to the LAR.

If dyad is self-responsible, prior to informed consent, the research assistant should evaluate the ability to provide informed consent of both PWD and FCG using The Evaluation to Sign an Informed Consent. If PWD, are deemed unable to consent, and have no designated LAR or POA, the research assistant should obtain written informed consent from the patient's next of kin in accordance with the UI IRB standard operating procedures for obtaining consent of human subjects with impairment in decision-making, specifically, in the order of spouse, adult child, siblings and relatives. Adequate time should be given for participants to process the information, and the research assistant should encourage participants to ask questions during the informed consent process.

Informed consent will be obtained from cognitively-intact caregivers using the protocol described above. If caregivers have legal guardians or power of attorney (POA), informed consent will be obtained from the responsible party. If the candidate caregivers are unable to consent and has no legal guardian or POA, the dyad will be excluded.

Either the self-responsible PWD, CG or his/her LAR will be asked to provide written informed consent

IV. Pilot study design Pilot study: was conducted December 2020 to March 2021

V. Stratification and Randomization

After informed consent, PWD will be assessed using the Dental Activities Test (DAT). Based on the DAT score, PWD and their FCG will be classified into 4 levels. Each level contains 10 dyads of PWD and FCG. All participants will be assigned to the intervention until we

reach 20 dyads then we will resume a control group. Each group has 5 dyads of PWD and FCG.

Table 3 Group assignment criteria

	9						
	Independent (DAT=9, N=10)	Needs Supervision (DAT=6-8, N=10)	Needs Assistance (DAT=3-5, N=10)	Full Care (DAT=0-2, N=10)			
Study group	5	5	5	5			
Control group	5	5	5	5			

VI. Oral Hygiene Intervention

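### The SAP plans rank-sum tests with no between-arm estimate or confidence interval; baseline enters only through change scores and DAT level not at all

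*SAP*

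**What the plan says.** The SAP (Statistical Analysis Plan) lists four things: descriptive statistics of participants at each visit; rank-sum tests to "compare continuous/numeric variables between the control and intervention groups at each visit"; Fisher's exact tests for categorical variables; and, for the primary outcomes, "Wilcoxon rank-sum tests were used to compare percent and raw score change in the primary outcomes between baseline and 4 weeks" and from baseline to 3 months. It makes no multiplicity adjustment. The SAP text available for this review names no effect measure, interval, covariate or stratum.

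The protocol plans for the data that an adjusted analysis would need. Section III says: "Data collection will occur at baseline, 4-weeks and 3 months". Table 5 shows this schedule for oral hygiene ("Plaque index Gingival index") and for several caregiver measures. Section V has DAT assessed after consent and used to form four levels of 10 dyads, 5 per arm.

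On assignment, Section V reads "All participants will be assigned to the intervention until we" and continues "reach 20 dyads then we will resume a control group". Section III sets the aim: group differences in PWD outcomes, caregiver outcomes "and the care partner relationship will be explored".

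**The concern.** An exploratory comparison of 20 v 20 dyads is useful mainly for the size of the difference and its uncertainty. A rank-sum p-value gives neither, and descriptive statistics by visit give no interval for the difference between arms. A reader who sees p > 0.05 could not tell whether a worthwhile effect has been excluded or the trial was too small to say. This part of the concern needs no assumption about effect size, correlation or score shape.

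The second part is precision. Subtracting baseline does not use it as efficiently as regressing on it when the correlation is moderate. The plan also groups dyads by DAT level and then leaves DAT out of the analysis.

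**Working it through.** **Inputs from the documents.** 40 dyads, 20 per arm, four DAT levels with 5 per arm in each; outcomes at baseline, 4 weeks and 3 months. The allocation is consistent: 4 × 10 = 40 and 4 × 5 = 20. The documents give no power or precision figure to reproduce.

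**Assumed inputs.** Two-sided 5% level, no dropout, score SD 1, near-normal score, baseline/follow-up correlation ρ, DAT share of variance s, true effect 0.8 SD where power is shown.

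**1. What a p-value hides.** At ρ = 0.5 the change score has SD √(2(1 − 0.5)) = 1. The half-width of a 95% interval is 2.024 × 1 × √(2/20) = 0.64 SD. An estimate of 0.1 SD would have an interval of −0.54 to 0.74, and an estimate of 0.5 SD one of −0.14 to 1.14. Both are non-significant, but they say different things. With SD 1, the difference detectable with 80% power is about 0.89 SD by the normal approximation, or about 0.91 SD for a rank-sum test.

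**2. Half-widths for the two analyses.**
- Hodges-Lehmann on raw change: about 2.024 × √(2(1 − ρ)) × √(2/20) × √(π/3).
- ANCOVA on baseline and DAT level, 34 residual df: about 2.032 × √((1 − s)(1 − w²)) × √(2/20), where w = (ρ − s)/(1 − s) is the within-level correlation.

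For ρ = 0.3 and s = 20%, the first is 2.024 × 1.183 × 0.316 × 1.023 = 0.78. For the second, w = 0.1/0.8 = 0.125 and 2.032 × 0.887 × 0.316 = 0.57. Simulated means, which agree with the formulas to within 0.01:

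| ρ, s | w | Raw change (SD) | ANCOVA (SD) |
|---|---|---|---|
| 0.3, 20% | 0.125 | 0.78 | 0.57 |
| 0.5, 20% | 0.375 | 0.66 | 0.54 |
| 0.7, 40% | 0.50 | 0.51 | 0.43 |
| 0.8, 20% | 0.75 | 0.42 | 0.38 |

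**3. Why ANCOVA cannot simply replace raw change.** The intervention arm is filled first, so the two cohorts may differ.
- A lasting gap of 0.5 SD, present at both visits, leaves raw change unbiased and biases ANCOVA by 0.5 × (1 − w). This is 0.44 SD at w = 0.125 and 0.10 SD at w = 0.8 (ρ = 0.8 with no DAT effect). With no treatment effect, raw change rejects about 5%, ANCOVA with DAT 10–31% and the visit-level tests 26–32%.
- A chance baseline gap of 0.3 SD biases raw change by 0.3 × (1 − ρ) = 0.21, 0.15 and 0.09 SD at ρ = 0.3, 0.5 and 0.7. Under a linear model it does not bias ANCOVA. Among simulated trials with a chance gap of 0.4–0.6 SD, raw change rejects 6–13% and ANCOVA 5–6%.

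**4. Power when both are reported.** In the order of the table, power is 53/67/87/97% for raw change and 78/83/95/98% for ANCOVA with DAT. If an effect is claimed only when both agree, it is 50/64/86/96%, no better than raw change. Claiming an effect when either is significant rejects 6.9–8.0% under the null.

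**5. Dependence on how DAT acts.** Steps 2 to 4 give DAT the same effect at both visits, so it cancels on subtraction. With no cohort gap, raw change then rejects 4.8–5.0% under the null. If DAT acts only at follow-up (ρ = 0.5, s = 20%), raw change rejects 2.6–3.1%. Power at 0.8 SD is then 68% for raw change, 83% for ANCOVA on baseline and 90% with DAT added.

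**The case against.** The best defence is that raw change suits this design. Filling the intervention arm first makes a lasting cohort difference the structural risk, and step 3 shows raw change to be the more robust test to it. That stands, and it is why raw change should stay in place and ANCOVA should only support it.

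It can also be said that baseline is already used through the change scores, that no passage says DAT predicts plaque or gingival index, and that the primary outcomes are never named. Some candidates are caregiver measures, for which a PWD's DAT level may matter little. These points stand too. Baseline and DAT are scheduled, but the documents do not report completeness. The SAP is in the past tense, so an added model may be post hoc, and it adds a test to a plan without multiplicity control.

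None of this answers the missing estimate and interval. A small exploratory study needs them more, and they require no new data.

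A reader might infer more than the documents support:
- *That the planned tests are invalid.* With no cohort gap, the change tests reject at most about 5% under the null in these models. The visit-level tests are conservative if the 5/5 quotas hold and DAT predicts outcome (1.2–2.9%).
- *That ANCOVA would raise the trial's power.* Co-reporting without picking the favourable p-value gives that gain up.
- *That DAT adjustment clearly matters, or clearly does not.* Step 5 shows that this turns on whether DAT affects both visits equally or predicts change, and the documents do not say.

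**Conclusion.** The point holds in a limited form. The SAP plans no between-arm estimate or interval for any primary outcome, so a non-significant result could not be interpreted. Baseline is used only through change scores, and DAT level is not used in the analysis.

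Reporting an interval for the raw-change difference is the main benefit. A baseline-adjusted interval would be narrower if the correlation is moderate (half-width about 0.57–0.43 against 0.78–0.51 SD for ρ = 0.3–0.7), with a small gain near 0.8. Every correlation, effect, gap size and DAT share behind these figures is assumed. The largest contrast needs a within-level correlation of only 0.125, so the loss of precision may be large or negligible.

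This is worth correcting, but it does not make the planned tests wrong. Neither analysis repairs the intervention-first assignment, which is a separate matter.

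**What to change.** 1. For each primary outcome, at 4 weeks and at 3 months, report the between-arm difference in raw change with a 95% confidence interval (for example Hodges-Lehmann) beside the existing rank-sum test.
2. Add as a supporting analysis an ANCOVA of the follow-up score on arm, baseline score and DAT level, with the adjusted difference and 95% interval. Use rank ANCOVA for the p-value if the score is skewed or ordinal. DAT may be dropped for caregiver outcomes. Label the analysis post hoc if results are known.
3. State that no effect will be claimed from whichever p-value is favourable, and that disagreement will be reported as such.
4. Treat percent change and the follow-up visit-level tests as descriptive. Percent change is undefined at a zero baseline, if a primary outcome can be zero.
5. State that, because the intervention arm is filled first, a lasting cohort gap biases ANCOVA, a chance baseline gap biases change, and neither analysis removes calendar-time or selection bias.

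The cost is a little more analysis work and four model degrees of freedom (baseline and three DAT indicators, leaving 34 residual). The two analyses may also disagree at the 5% level: in 4–6% of simulated trials under the null, and in 31/21/10/2% at a 0.8 SD effect for the four tabulated cases. No new data are needed.

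### The SAP tests raw and percent change side by side without adjusting for baseline or DAT level; one baseline-adjusted comparison per outcome and follow-up would be more efficient if the arms were randomised

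*SAP*

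**What the plan says.** The SAP (Statistical Analysis Plan section) has two layers of between-arm testing. In the first, "Wilcoxon rank-sum tests were used to compare continuous/numeric variables between the control and intervention groups at each visit". In the second, Wilcoxon tests "compare percent and raw score change in the primary outcomes between baseline and 4 weeks and baseline and 3 months". It adds: "No adjustments have been made for multiple comparisons". The visible text names no covariate, no DAT-stratified analysis, no key outcome or time point, no alpha, and no rule for choosing between raw and percent change. Part of the SAP was not available, so these absences are judged on the visible text only.

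The protocol supplies the data that an adjusted analysis needs. Section V states: "Based on the DAT score, PWD and their FCG will be classified into 4 levels". Its Table 3 shows 5 dyads per arm at each level. Table 5 lists "Plaque index Gingival index" under oral hygiene, measured at baseline, 4 weeks and 3 months. The visible text does not say that these are the primary outcomes.

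Two tensions in the protocol bear on the point. Section III says Aim 2 will examine the "efficacy and feasibility of the proposed intervention using a randomized controlled design among 40 PWD/CG pairs", but also that differences in patient outcomes, "caregiver outcomes (e.g., burden, self-efficacy) and the care partner relationship will be explored". Section V, under a heading that includes randomization, says "All participants will be assigned to the intervention until we" have 20 dyads, with the control group to follow.

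**The concern.** A change score subtracts baseline, which fixes the baseline slope at 1 whatever the true correlation between visits. A regression on baseline estimates that slope. In a randomised trial of 40 dyads the difference matters in two ways: the change score is noisier, and it is pulled off target when the arms happen to differ at baseline.

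Running raw and percent change together adds an ambiguity. The two can give different verdicts on the same outcome at the same visit, and the reader cannot tell which one the plan would have relied on.

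Two changes tested at two times make four change tests per primary outcome, before the per-visit tests are counted. That matters only if a single significant result is read as showing efficacy.

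**Working it through.** **Inputs.** From the protocol: 20 dyads per arm (section III), four DAT levels with 5 dyads per arm in each (Table 3), and a baseline with two follow-ups (Table 5). Not in the documents and so assumed: two-sided alpha 0.05, effect d in units of the single-visit SD, equal SDs across visits, visit correlation r, no dropout, randomised arms. The visible documents contain no power calculation, so there is no figure to reproduce.

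**Step 1: normal theory.** In SD² units, the variance is 2(1 − r) for raw change and 1 − r² after baseline adjustment. The ratio of adjusted to raw is (1 + r)/2 = 0.65/0.75/0.85 at r = 0.3/0.5/0.7. So 40 dyads analysed by raw change carry the information of 40 × ratio = 26/30/34 dyads analysed with adjustment.

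For d = 0.8 and r = 0.5:
- Raw change: SE = √(1 × 2/20) = 0.316; 0.8/0.316 = 2.53; power = Φ(2.53 − 1.96) = 72%.
- Adjusted: SE = √(0.75 × 2/20) = 0.274; 0.8/0.274 = 2.92; power = Φ(2.92 − 1.96) = 83%.

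**Step 2: simulation of the actual tests** (20,000 trials per correlation for the four d = 0.8 rows below). The small sample and the rank test lower both figures.

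| Test, d = 0.8 | r = 0.3 | r = 0.5 | r = 0.7 |
|---|---|---|---|
| Wilcoxon, raw change | 53% | 67% | 87% |
| Wilcoxon, percent change | 56% | 70% | 89% |
| Model with baseline and DAT level | 72% | 80% | 92% |
| Same model on ranks | 70% | 77% | 89% |

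Other inputs, raw change v adjusted model:
- r = 0.5: 33% v 43% at d = 0.5, and 85% v 94% at d = 1.0.
- r = 0.8, d = 0.8: 97% v 98%.
- 18 per arm (r = 0.5, d = 0.8): 62% v 74%.

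The gain comes from baseline. With a DAT level that does not predict outcome, power is 79.6% with DAT in the model and 79.9% without (r = 0.5). If DAT is assumed to explain 20% of the variance, adjusted power is 77/83/94%.

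Raw and percent verdicts disagree in 3–13% of simulated trials per outcome and time.

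**Step 3: baseline differences, chance or systematic.** Let the arms differ by b at baseline, with no treatment effect.
- *Chance difference.* The expected follow-up difference is rb. Raw change leaves −(1 − r)b; adjustment leaves 0. The chance of |b| > 0.5 SD is 2[1 − Φ(0.5/0.316)] = 11%. In those trials the false-positive rate is 17/13/10% for raw change and 5% for the adjusted model.
- *Stable difference*, as could arise if the arms were enrolled one after the other. The follow-up difference is b. Raw change leaves 0; adjustment leaves (1 − r)b, which is 0.35/0.25/0.15 SD for b = 0.5 SD. The simulated false-positive rate is about 19/13/9% for the adjusted model and 5% for raw change.

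**Step 4: multiplicity.** The four change tests per outcome are correlated, so the independent-test value of 1 − 0.95⁴ = 19% is too high. Simulated over a range of correlations with no effect, the chance of at least one p < 0.05 is 10–12% for one outcome, and 17–21% over eight change tests if two outcomes are assumed. Four adjusted tests (two outcomes, two times) still give 15–18%, so adjustment alone does not deal with multiplicity.

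**The case against.** The best reply is that a rank test on change is valid with 20 randomised dyads per arm. Taken over all trials it holds about 5%, and the inflated rates in Step 3 apply only to the 11% of trials with a large chance imbalance. That stands: under randomisation the issue is efficiency and clarity, not an invalid test.

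The gain is also smaller against the best test already in the plan. At r = 0.3 the per-visit Wilcoxon at follow-up has about 67% power, against 72% adjusted. At r = 0.7 the rank version of the model only equals percent change, at 89%. These limits stand too.

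The allocation objection is the most serious. If section V describes what happened, the argument for adjustment can reverse, as Step 3 shows. A reader might infer that adjustment is the safer choice however the trial was run; the documents do not support that.

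Nor do they support three other readings that come easily:
- That this trial has 67% power and would have 80%. Those figures need inputs that the documents do not give.
- That the plan disregards baseline. Change scores use it, and the per-visit comparisons include the baseline visit.
- That one significant p-value will be presented as efficacy. The SAP discloses the lack of adjustment, section III uses the language of both efficacy and exploration, and nothing visible says how a single result would be read.

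**Conclusion.** The point holds as a minor-to-moderate weakness in the choice of analysis. Each primary outcome is tested on two change scales at two times, with no visible rule for which scale governs and no adjustment for baseline or DAT level.

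For an assumed 0.8 SD effect in randomised arms, adjustment adds about 19/13/5 points of power over raw change at r = 0.3/0.5/0.7 (72 − 53, 80 − 67, 92 − 87), and about 2 points at r = 0.8. These are conditional illustrations, not properties of this trial. If allocation was sequential, neither approach is unbiased, and which one errs less depends on whether the arm difference is chance or stable. Multiplicity is a secondary matter of labelling.

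**What to change.** 1. For each primary outcome at each follow-up, make the main comparison one model of the follow-up value on arm, baseline value and DAT level, on ranks if the data are skewed. Report the adjusted difference with a 95% CI. Keep raw change as a sensitivity analysis and drop the percent-change test.
2. Reconcile sections III and V of the protocol on allocation and state what was done. If the arms were filled in sequence, show adjusted and raw-change estimates together and say that neither removes confounding by enrolment period.
3. Name the primary outcomes, label the between-arm comparisons exploratory, and report the rest, including the per-visit ones, as estimates with 95% CIs. The SAP is written in the past tense; if outcome data had already been seen, disclose that the change of model is post hoc.

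**Cost.** Two outcomes would need four small models, each with 40 − 6 = 34 residual degrees of freedom, on variables already scheduled for collection. Fewer results could be called significant. The exploratory label costs no power but gives up a formal efficacy claim. Keeping that claim by applying Holm over four adjusted tests would hold the familywise error at 4–5%, but would cut power at one outcome and time from 80% to about 62% (d = 0.8, r = 0.5). That is below the 67% of the unadjusted raw-change test, so it is a real trade-off. None of these steps repairs the allocation conflict itself.
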